The overall goal of this project is to investigate the mechanisms of optimized tDCS via two important markers of chronic pain, conditioning pain modulation (CPM) and slow temporal summation (STS). In addition, the results of this study will represent a significant step toward developing a novel low-cost therapy for FM and validating a therapeutic novel target.

Sponsors

This study is funded by NIH-NCCIH (1 R01 AT009491-01A1).

II. SPECIFIC AIMS

This trial aims at understanding the mechanisms of optimized tDCS (16 tDCS sessions combined with exercise) on pain control. Optimized tDCS can lead to stronger engagement of the endogenous pain regulatory system that will ultimately lead to increased pain relief in patients with FM. Therefore, we designed a 2x2 factorial mechanistic trial [tDCS (active and sham) and aerobic exercise (active and control)] to test the following aims:

Aim 1 (primary outcome): Evaluate the effects of 4 weeks of tDCS coupled with exercise on the endogenous pain regulatory system assessed by CPM and central sensitization as assessed by TSPS, and compared to either intervention alone and to no intervention. *We hypothesize that tDCS coupled with exercise will result in restoration of pain endogenous regulatory system as indexed by greater decrease in SPS and increase in CPM responses. We also hypothesize to observe differences between groups as exercises may have a larger effect on the insula and somatosensory cortex (which is indexed by SPS) while tDCS seems to have a greater effect on prefrontal and*

cingulate cortex (which is indexed by CPM). Thus, these markers will be important to understand to what extend the nodes of pain matrix may be more involved in pain relief and whether the effects of tDCS and exercises are mainly mediated by an increase in inhibition (increase of CPM) or a decrease of excitation (decrease of TSPS).

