Aim 2: Determine the effect of these interventions on cortical markers of inhibitory control that are also affected in FM, such as intracortical inhibition as assessed by transcranial magnetic stimulation (TMS) and changes in thalamocortical dysrhythmia as assessed by EEG. *We hypothesize that active tDCS combined with exercise will result in greater increases in intracortical inhibition as measured by the short intracortical inhibition (SICI). These increases will be associated with greater reduction of pain when compared to either intervention alone. We also hypothesize that tDCS combined with exercise will induce a greater decrease in theta power than any intervention alone, as well as to the control group. Therefore, we hypothesize that decreases in theta EEG band power could be used as a marker of the normalization of the thalamic dysrhythmia normalization.*

Aim 3: Assess the number of sessions needed to induce significant changes in markers of endogenous pain inhibitory system and central sensitization (CPM and TSPS) and cortical changes (as indexed by paired pulse TMS and EEG). *We hypothesize that the group receiving the top-down and bottom-up strategies (tDCS and AE) will have a greater number of subjects with target engagement (change of at least 30% as compared to baseline) of pain and cortical marker.*

Sub-aim 3: Assess whether engagement of the two main targets tested in this study – TSPS and CPM – are associated with the secondary clinical outcomes (i.e., changes in pain outcomes: Brief Pain Inventory, Revised Fibromyalgia Impact Questionnaire). *We hypothesize that changes in TSPS and CPM will be correlated with these pain outcomes. We also hypothesize to find a correlation between baseline values of TSPS and CPM and pain relief immediately after the intervention.* This result will be important as to assess the suitability of such markers as potential treatment response predictors.

[figure not shown]
III MEDICAL MONITOR

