- 7) current opiate use in large doses (more than 30mg of oxycodone/hydrocodone or 7.5mg of hydromorphone (Dilaudid) or equivalent),
- 8) Patients will be excluded when they have increased risk for exercise as defined as (i) not fulfilling the american college of sports medicine (acsm) criteria (i.e., risk of cardiovascular complication [30]) and in this case not cleared by a licensed physician.

[figure not shown]
[figure not shown]
[figure not shown]
(If a patient meets the inclusion criteria but is found to have a risk factor (according to the ACSM guidelines), he/she will undergo a medical visit in order to obtain clearance. If he/she does not pass the medical clearance, he/she will not be included in the study.

[figure not shown]
V. SUBJECT ENROLLMENT

Subjects will be sought through the following sources:

- Attending physicians, therapists, clinicians and other healthcare providers may refer out subjects to the study.
- We will provide them with study information sheets and flyers. Prospective subjects will be encouraged to contact the study co-investigators.
- Flyers posted in the outpatient specialist clinics and public posting boards (i.e., digital signage).
- Internet (i.e., Google Ads) and newspaper advertisements.
- Advertisings posted in public transportation (The T).
- Via the Partners Healthcare Research Patient Data Registry (RPDR), Patient Gateway, and Research Match (Vanderbilt Recruitment Tool).
- Potential subjects might also be identified through their medical records (epic LMR, etc.) and their physicians might be asked to inform the subjects about the study.
- Support groups presentations.

Detailed Protocol 7

The method of randomization is a 1:1:1:1 permuted block randomization, generated by a web-based randomization tool. Randomization order will be kept in individual sealed and opaque envelopes with order of entrance and the randomization master list will be kept in a locked drawer; therefore, subjects will get their assignment according to the order of entrance in the study.

[figure not shown]

Figure 1 - Intervention groups with 1:1:1:1 allocation ratio.

Blinding Procedure:

Participants, family members, treating staff/ physicians, data collectors, site investigators and the statistician will be blinded to group stimulation assignment.

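### Sub-aim 3 plans to correlate change in CPM/TSPS with change in pain and specifies no conditioning on arm; a correlation pooled over the four arms could show a link where none exists within arms

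*Combined protocol and SAP*

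**What the plan says.** The design, in Section II, is a "2x2 factorial mechanistic trial [tDCS (active and sham) and aerobic exercise (active and control"), and the section on enrollment states: "The method of randomization is a 1:1:1:1 permuted block randomization". There are therefore four equal arms.

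Sub-aim 3 asks whether engagement of TSPS and CPM "are associated with the secondary clinical outcomes (i.e., changes in pain outcomes: Brief Pain Inventory, Revised Fibromyalgia Impact Questionnaire"). Its hypothesis is that "changes in TSPS and CPM will be correlated with these pain outcomes". The sub-aim has a second part, on baseline TSPS and CPM as correlates of later pain relief, and says the result is needed to "assess the suitability of such markers as potential treatment response predictors". This point concerns only the first part, change against change.

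Aim 1 adds a mechanistic purpose: to learn "whether the effects of tDCS and exercises are mainly mediated by an increase in inhibition (increase of CPM) or a decrease of excitation".

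The readable text of Section VIII does not mention Sub-aim 3. Its nearest items are a path analysis, in which CPM and TSPS are the outcomes and improvement in secondary outcomes is the intermediate step, and a test of whether secondary clinical variables moderate the interventions' effects on the mechanistic outcomes.

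**The concern.** Correlation is the only method named for relating marker change to clinical change. Over all subjects in a four-arm trial, such a correlation has two parts: the association among patients within an arm, and the association among the four arm means. The second part exists whenever the same arms shift both variables, even if no patient's pain relief has anything to do with that patient's change in CPM or TSPS.

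The sponsor's own expectations make this plausible. Section I credits both tDCS and aerobic exercise with analgesic effects and with reducing dysregulation of inhibitory control, and says the combination relieved pain more than either alone. Aim 1 expects the combined arm to move CPM and TSPS most.

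At stake is the trial's link between moving the target and clinical relief. When the arms shift marker and pain in the hoped-for directions, the artefact favours the hypothesised link.

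**Working it through.** **Inputs from the documents.** Four equal arms; 116 subjects (29 per arm); effect size 0.90 used for the sample size, from a quoted range of 0.9 to 1.26; two-sided alpha 0.05; power 85%; dropout 20% (Section VIII).

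**Assumptions.** The documents give no effect size for pain, so a range is shown. Effects are in within-arm SD units of the change scores. The within-arm correlation is set to exactly zero.

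**The plan's own figure.** The normal approximation gives n per arm = 2(1.960 + 1.036)²/0.90² = 22.2, so 23. Allowing for dropout, 23/0.8 = 28.75, so 29, and 4 × 29 = 116. The stated total reproduces. Completers are taken as 4 × 23 = 92.

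**Correlation created by arm alone.** With arm means m_x (marker) and m_y (pain), unit within-arm SD and equal arms:

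r = cov(m_x, m_y) / √[(1 + var m_x)(1 + var m_y)]

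Arms are ordered control, tDCS alone, exercise alone, combined. Signs are set so that improvement is positive.

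- Additive, both effects 0.90: means 0, 0.45, 0.45, 0.90 on each; var = cov = 0.101; r = 0.101/1.101 = 0.09.
- Only the combined arm moves, both 0.90: var = cov = 0.81 × 3/16 = 0.152; r = 0.152/1.152 = 0.13.
- One factor drives both, 0.90: var = cov = 0.81/4 = 0.2025; r = 0.2025/1.2025 = 0.17.
- Additive, marker 0.90 and pain 0.3: cov = 0.034; r = 0.034/√(1.101 × 1.011) = 0.03.
- Additive, both 1.26: var = cov = 0.198; r = 0.198/1.198 = 0.17.
- Marker responds only to tDCS and pain only to exercise: cov = 0; r = 0.

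**How often a 5% test rejects.** Trials were simulated with independent normal errors plus these arm means, using the pooled Pearson test (100,000 trials per row, 92 completers):

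| Pattern | Marker, pain effect (SD) | Pooled r | Pooled test rejects |
|---|---|---|---|
| Additive | 0.90, 0.3 | 0.03 | 6% |
| Additive | 0.90, 0.90 | 0.09 | 14% |
| Only combined arm moves | 0.90, 0.90 | 0.13 | 24% |
| One factor drives both | 0.90, 0.90 | 0.17 | 37% |
| Additive | 1.26, 1.26 | 0.17 | 35% |
| Different factors | 0.90, 0.90 | 0.00 | 5% |

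A Fisher-z check of the second row: 0.092 × √(92 − 3) = 0.87, and P(Z > 1.96 − 0.87) + P(Z < −1.96 − 0.87) = 0.138 + 0.002 = 14%.

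With all 116 subjects the problem is somewhat larger: with both effects at 0.90, about 17% to 45% across the three shared patterns.

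**With arm removed.** Centring both changes on their arm means (residual df = N − 5) brings rejection back to about 5% in every row.

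**The case against.** Several points on the other side have force.

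- **The plan does not specify a pooled, unadjusted correlation.** A reader might infer that it does. The sentence is a hypothesis, and nothing says the correlation is taken over all subjects ignoring arm. The supportable statement is that no conditioning on arm is specified. Some figures and later pages are not readable in the text reviewed, so a specification there cannot be excluded.
- **Section VIII has a path analysis that includes treatment.** This is relevant: in a linear model, the test of no marker–pain association given arm is the same whichever variable is the outcome. But that analysis centres on the combined intervention, runs from clinical improvement to CPM/TSPS, and is not tied to Sub-aim 3. It covers the gap in part at most.
- **A false link is not inevitable.** A reader might infer that two unrelated treatment effects would by themselves produce one. The figures support only that they could: under the additive pattern the pooled test fails to reject in 86% of trials at 0.90 SD. The artefact also vanishes if marker and pain respond to entirely different factors. Aim 1 does expect different emphases, for instance that "exercises may have a larger effect on the insula and somatosensory cortex (which is indexed by SPS"), with tDCS acting more on CPM. However, it speaks of larger and greater effects, not exclusive ones. With opposing 2:1 weights (marker means 0, 0.6, 0.3, 0.9; pain means 0, 0.3, 0.6, 0.9), r = 0.09/1.1125 = 0.08 and rejection is about 12%.
- **The correlation is not the trial's evidence of engagement.** A reader might take it so, but Aim 3 defines engagement separately, as a change of at least 30% from baseline. The correlation bears on whether engagement goes with clinical benefit.

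**Conclusion.** The point holds in this form: the change-against-change part of Sub-aim 3 rests on a correlation with no conditioning on arm specified, and the pooled version could report a marker–pain link that is only a by-product of randomised arms differing on both. Over the patterns tabulated, with 92 completers, the false-positive rate runs from about 5% to 37% instead of 5%. Where it falls depends on the unknown pain effect and on how far marker and pain follow the same arms; only when they do does the bias grow with the treatment effect. These figures assume equal arms, normal change scores and zero within-arm association.

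This should be corrected, but it is a secondary matter. It does not affect the primary comparisons of CPM and TSPS between arms, or the use of baseline CPM and TSPS as predictors.

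**What to change.** Add to Section VIII, for the change-against-change part of Sub-aim 3:

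- Regress BPI change (and, separately, FIQ-R change) on CPM change (or TSPS change), with tDCS, exercise and their interaction, and the baseline values of both marker and clinical outcome.
- Report the common within-arm slope with a 95% CI, and check that slopes are similar across the four arms before relying on a single one.
- Do not use an unadjusted pooled correlation as evidence that target engagement is linked to clinical benefit.
- State how this analysis relates to the path analysis already planned.

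The cost is a short addition to the text, three degrees of freedom for arm (plus one for each baseline) and no new data. A partial correlation given arm alone would also remove the artefact, but it is not the same analysis because it omits the baselines. Neither removes other confounding between marker and pain, so the slope should be described as an association and not as proof of mediation.

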Chronic pain results from an imbalance between excitatory and inhibitory pain pathways. Recent evidence has suggested that pain inhibitory pathways are affected in FM; thus, further understanding these pathways' role in FM can significantly change how FM is treated. Two assessments can test pain inhibitory activity: Temporal Slow Pain Summation (TSPS) and

conditioned pain modulation (CPM). During TSPS, the progressive increase in pain intensity following repetition of identical nociceptive stimuli reflects C-fiber and other central neurons temporal summation and has been used as a marker for pain sensitivity. TSPS does not seem dependent on increased impulse C-fiber input, suggesting that TSPS is a CNS phenomenon rather than peripheral [8]. As a CNS phenomenon, several mechanisms contribute to TSPS, including ineffective central pain modulation [9] and rostral ventromedial medulla facilitation [10]. Moreover, TSPS is thought to rely on the same mechanisms that underline the initiation and maintenance of several chronic pain conditions, and thus TSPS has also been widely studied in FM [11, 12]. FM patients also demonstrate lower CPM inhibitory efficacy. Indeed, the rate of patients with FM reporting pain facilitation during CPM has been found to be significantly increased compared with that of the controls (41.7% vs 21.2%) [13]. Based on the current literature, there is strong evidence that for some FM patients the endogenous pain regulatory system is impaired. Moreover, CPM efficacy has already been related to pain development 6 months after surgery [14], making it another suitable marker for response prediction.

There is also evidence of CNS changes in FM that are associated with a deficit in the inhibitory control, namely abnormal cortical excitability as expressed by decreased short intracortical inhibition (SICI) and facilitation (SICF) and increased resting motor threshold [15]. This is thought to reflect an inhibitory deficit that is associated with altered thalamic anatomy and activity [16], which may result in abnormal thalamocortical circuits, as evidenced by the association between central pain and thalamic dysrhythmia [17-19]. Therefore, the unravelling of inhibitory deficits underlying pain maintenance mechanisms in patients with FM can also help the development of novel interventions for this pathology, as well as for other chronic pain conditions associated with a deficit in the regulatory pain system.

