**Visits 0 and 1 may be completed in the same day or broken up into two separate visits as the subject prefers*

Daily pain reports will be collected for the two weeks between V1 and V2.

VISITS 1.1 – 1.3: Subjects will be randomized during visit 1.1. The two groups will participate in a different conditioning exercise program for two weeks according to their group assignment (see section VI). At visits 1.1, we will conduct assessments of pain, quality of life, TPSP, CPM, TMS and EEG acquisition (we will offer the possibility of splitting this visit into two visits if the subject gets too tired). At visit 1.3, we will conduct assessments of pain and quality of life, TPSP and CPM. In all these visits we will conduct AE adverse effects questionnaires.

VISITS 2, 11, 17: assessments of pain (except visit 2), quality of life (except visit 2), TSPS, CPM, TMS and EEG acquisition. At the same visit, tDCS and AE will be performed. Also, tDCS and AE adverse effects questionnaire.

VISITS 6 and 14: tDCS, AE, tDCS and AE adverse effects questionnaire, CPM, TSPS, assessments of Pain

[figure not shown]
VISITS 3, 5, 8, 10: tDCS only and tDCS adverse effect questionnaire. The subjects will have the option of choosing to do the visits remotely home-based tDCS (Soterix Medical 1X1 tDCS mini-CT stimulator device), in order to decrease the burn of daily visits at our site.

[figure not shown]
VISITS: 4, 7, 9, 12, 13, 15, 16: tDCS, AE and tDCS and AE adverse effects questionnaire.

VISIT: 18: Pain and quality of life assessments, TMS, EEG, CPM, TSPS.

[figure not shown]
Replacement of missed sessions (though all the effort will be made to avoid missing sessions) will be allowed to up to 20% of missed sessions (up to 4 total visits) according to the treatment schedule. Follow-up and assessments will be encouraged even if more than 20% of missed sessions given data will be analyzed as ITT (though we expect this to be low). We will allow the following visit windows:

- *between visit 1 and 1.1: 2 weeks*
- *between visits during the conditioning period (from visit 1.1 to 1.3): 2 weekdays*
- *between visit 1.3 and visit 2: up to 1 week*
- *between visit 17 and visit 18: up to 2 weeks (before or after the final follow-up, meaning visit 18 could happen 2.5 months to 3.5 months from visit 17)*
- *between Visit 2 and Visit 17: up to 6 weeks*

[figure not shown]

Detailed Protocol 16

Detailed Protocol 17

VII. DESCRIPTION OF ASSESSMENTS

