Sample Size Calculation: This study's original sample size calculation was based on an expected effect size of 0.78, with 85% statistical power and a significance level of 0.05. However, after 6 years of the original sample size calculation (it was done in 2017 upon grant submission, see appendix 2), we have observed in our recent study in collaboration with other colleagues and recent meta-analyses effect sizes ranging from 0.9 to 1.26, which are larger than we initially anticipated. Considering this new information, we re-estimated the sample size to ensure we do not expose subjects to the burden of participating in a study that involves a placebo arm. Also, this would make the study feasible to be completed in the 5-year period of this grant, given our recruitment was significantly affected by the COVID pandemic, especially in the years 2020 and 2021. We have recalculated the sample size using the smallest reported effect size (0.90) using the t-test calculation for the difference between two independent means (to test for the main hypothesis) – this is the same method used in the original sample size calculation; and determined that we need a total of 116 participants (29 in each group) to achieve 85% power (as planned before). We assumed a type I error of 5% (alpha), and a type 2 error of 15% (beta). We also made this calculation considering the same parameters used in the original sample size calculation, such as dropout rates of 20%. The sensitivity analysis for the sample size calculation is summarized in the table below.

[figure not shown]
Therefore, we reduced the sample size from 148 to 116 participants, which will maintain the same planned statistical power (85%). This revised sample size will allow us to detect the more precise effect sizes currently reported in the literature and will also make the study feasible to be completed on time, given the large impact of the COVID pandemic on our study.

[figure not shown]
Planned Analysis:

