The primary analysis: All the analyses will be performed as intention-to-treat in which all subjects undergoing randomization who receive at least one intervention session (randomization will take place immediately before the first intervention) will be included. We will conduct sensitivity analyses and test different models of handling missing data (LOFC and MI). The change in the primary efficacy endpoint, CPM (and also TSPS), from baseline to week 4 will be tested with a mixed linear model. This model will be adjusted for important demographic variables (i.e., gender) and also baseline clinical parameters where appropriate. All tests will be two-sided (alpha level, 0.05). We will initially test our main hypothesis that the combined treatment induces a greater increase in CPM (and decrease in TSPS) as compared to the control condition. If the effect is significant, we will then test differences between the combined group vs these two interventions alone.

[figure not shown]
In order to understand the time effect of this intervention (using the secondary endpoints added in this model (week1 and follow-up)), we will run a secondary mixed linear model to estimate the rate of change over time by also including an interaction between treatment and time as to detect whether treatment effect changes differently according time. If the interaction is not significant we will then test whether there is a main effect of time that is independent of treatment level (interaction will be then removed from the model). We will adjust this model for important covariates such as age, gender, pain levels (numeric pain scale – NPS), and other baseline clinical outcomes where appropriate. For the secondary clinical variables with a significant effect we will also test whether they moderate the interventions' effects on our mechanistic outcomes, thereby gaining additional mechanistic insights.

To complete our analysis, we will apply a path analysis [1, 2] to the outcome data (CPM and TSPS) to determine if endogenous pain modulation changes (as indexed by CPM and TSPS) associated with the combined intervention (tDCS and AE) is related to direct effects versus indirect effects through improvements in secondary outcomes. We propose that a direct effect of tDCS and AE on the endogenous pain inhibitory system can be inferred if the treatment effect cannot be explained by changes in psychological or functional outcomes.

[figure not shown]

[figure not shown]
Detailed Protocol 23

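### Sub-aim 3 would assess baseline CPM and TSPS as treatment-response predictors from a correlation with pain relief, which cannot separate prediction from prognosis

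*Combined protocol and SAP*

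**What the plan says.** Section II, Sub-aim 3 of the combined protocol and SAP has two correlational hypotheses. The first concerns changes: "We hypothesize that changes in TSPS and CPM will be correlated with these pain outcomes", where the pain outcomes are the Brief Pain Inventory (BPI) and the revised Fibromyalgia Impact Questionnaire (FIQ-R). The second concerns baseline values: "We also hypothesize to find a correlation between baseline values of TSPS and CPM and pain relief immediately after the intervention". The next sentence gives its purpose: "This result will be important as to assess the suitability of such markers as potential treatment response predictors". Neither hypothesis says whether the correlation is pooled or taken by arm, and neither mentions adjustment.

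Section I (Background) takes a similar step: "CPM efficacy has already been related to pain development 6 months after surgery [14], making it another suitable marker for response prediction".

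The readable text of Section VIII, Planned Analysis, contains these related analyses:
- a primary mixed model with CPM (and TSPS) as the outcome;
- a secondary mixed model that estimates change over time "by also including an interaction between treatment and time as to detect whether treatment effect changes differently according time";
- a test of whether secondary clinical variables moderate the effect of the interventions on the mechanistic outcomes;
- a path analysis of CPM and TSPS.

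None has pain as the outcome with baseline CPM or TSPS as the effect modifier.

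**The concern.** A prognostic marker tells us who will improve whatever they receive. A predictive marker tells us who gains more from active treatment than from control. A correlation between baseline marker and relief responds to both. Pooling the arms does not separate them, and neither does restricting to the combined arm, because relief in an active arm includes natural course, placebo response and regression to the mean. The comparison that separates them is the marker slope under active treatment against the slope under control. The 2x2 design provides the control arms, but the plan does not say they will be used for this question. The Background sentence on post-surgical pain shows the same gap: an association with later pain after surgery is prognostic, yet it is offered as a reason to expect response prediction.

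The correlation between changes has a related weakness. If it is pooled without adjustment for arm, two outcomes that both respond to treatment will correlate across arms even when they are unrelated within patients.

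At stake is a claim that CPM or TSPS identifies patients who benefit from treatment, when the same result would arise from a marker with no such property.

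**Working it through.** **Inputs from Section VIII.** 116 participants, 29 per arm; effect size 0.90, the smallest in "effect sizes ranging from 0.9 to 1.26"; 20% dropout; two-sided alpha 0.05; power 85%. The sizing reproduces: 2 × (1.960 + 1.036)² / 0.90² = 22.2, so 23 per arm; 23 / 0.8 = 28.75, so 29; 29 × 4 = 116. Completers are therefore taken as 29 × 0.8 ≈ 23 per arm, 92 in total.

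**Assumed, because the documents give no value.** The within-arm marker–relief correlation r is 0.2, 0.3 or 0.4 and is the same in every arm. Treatment adds 0.45 SD of relief for tDCS and 0.45 SD for exercise, so 0.90 SD for the combination.

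**1. Purely prognostic marker.** Simulation with 6,000 trials per setting. The interaction model has tDCS, exercise, tDCS-by-exercise, marker, marker-by-tDCS, marker-by-exercise and baseline pain. Share of trials with p < 0.05:

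| Test | r = 0.2 | r = 0.3 | r = 0.4 |
|---|---|---|---|
| Pooled correlation, n = 92 | 44.8% | 80.2% | 96.8% |
| Correlation in combined arm, n = 23 | 14.3% | 29.3% | 48.7% |
| Marker-by-tDCS | 4.7% | 5.5% | 5.2% |
| Marker-by-exercise | 4.9% | 4.8% | 4.9% |
| Marker-by-combined-versus-control | 5.0% | 4.7% | 5.2% |

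Hand check at r = 0.3. The between-arm variance is 0.5 × 0.45² = 0.101, so the pooled r is 0.3 / √1.101 = 0.286. Fisher's z gives atanh(0.286) × √89 = 2.77, and Φ(2.77 − 1.96) ≈ 79%. With no dropout (29 per arm) the pooled row becomes 53%, 88% and 99%, and the combined-arm row 18%, 36% and 61%.

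**2. The converse.** Take a marker with correlation +0.5 under active tDCS and −0.5 under sham, 29 per arm. The mean pooled correlation is about 0 and is significant in 8% of trials. The combined-versus-control interaction is significant in 98%. A correlation can therefore miss a true predictor as well as endorse a false one.

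**3. Regression to the mean alone.** Let the marker correlate 0.3 with baseline pain, and let pain have test–retest correlation ρ. The marker's correlation with relief is then 0.3 × √((1 − ρ)/2), which is 0.116 at ρ = 0.7 and 0.150 at ρ = 0.5. In simulation the pooled correlation is significant in 20.8% and 29.8% of trials, falling to 5.7% and 4.8% with baseline pain in the model.

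**4. Change with change, no within-patient link.** The arm effects, in SD, are applied to both outcomes. If v is the between-arm variance, the spurious pooled correlation is v / (1 + v). For 0/0.45/0.45/0.90, v = 0.101 and r = 0.09. For 0/0/0/0.90, v = 0.90² × 0.25 × 0.75 = 0.152 and r = 0.13. Simulation, 8,000 trials:

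| Arm effects (SD) | Unadjusted | Adjusted for arm |
|---|---|---|
| 0 / 0.45 / 0.45 / 0.90 | 14.2% | 4.8% |
| 0 / 0 / 0 / 0.90 | 23.5% | 4.9% |
| 0 / 0.63 / 0.63 / 1.26 | 35.9% | 5.1% |
| 0 / 0 / 0 / 1.26 | 61.9% | 5.3% |

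**5. What the interaction test can deliver.** The mean standard errors are 0.221 (tDCS, 46 v 46) and 0.316 (combined versus control, 23 v 23). The 95% CI half-widths are about 0.44 and 0.64 SD of relief per SD of marker. Power for a slope of 0 versus 0.3 is 26.1% and 15.7%; for 0 versus 0.6 it is 77% and 46%. Testing both factorial interactions gives 1 − 0.95² ≈ 10% chance of at least one false positive per marker and outcome.

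**The case against.** The best reply is that the plan is silent rather than wrong. If correlations were shown separately for all four arms, the sham and control arms would be visible and the controls would be used, at least descriptively. This stands in part: the text does not rule it out. But four separate correlations are not a test of a difference in slopes. With r = 0.3 in every arm, the chance that the combined arm is significant and the double control is not is 0.293 × (1 − 0.293) ≈ 21%, for a marker that predicts nothing.

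Other points have weight:
- The wording is cautious, and this is a sub-aim on secondary outcomes.
- Section I elsewhere describes an earlier tDCS trial in effect-modification terms, and Section VIII includes a moderation test, so the idea is not foreign to the team. That test runs the other way, with CPM and TSPS as outcomes.
- Figures are missing from the readable text, and an interaction could be described there. The finding is therefore limited to what can be read.
- The correlations are assumed. The highest change-with-change rates need tDCS alone and exercise alone to have no effect, although Section I reports analgesic effects for both; the additive rows are the more cautious ones. Section VIII does not tie the 0.9 to 1.26 range to a named outcome.
- The interaction test has low power. That argues for modest claims, not for resting the claim on a different quantity.

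**Conclusion.** The concern holds. Sub-aim 3 names a correlation and says what it will be used for, and the correlation cannot support that use. The readable analysis plan has nothing that fills the gap. With 23 completers per arm and assumed correlations of 0.2 to 0.4, a purely prognostic marker passes the pooled test in 45% to 97% of trials and the combined-arm test in 14% to 49%, against about 5% for each interaction. The percentages depend on those assumptions; the inability to separate prognosis from prediction does not. Unadjusted change-with-change correlations would be falsely significant in 14% to 24% of trials at 0.90 SD and 36% to 62% at 1.26 SD. The consequence is confined to the interpretation of a secondary, hypothesis-generating result. The primary comparison is not affected.

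**What to change.** Specify the Sub-aim 3 analysis in Section VIII:

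- For each marker, over all four arms, model change in BPI pain to visit 17 (week 4), and FIQ-R where collected, on tDCS, exercise, tDCS-by-exercise, the marker, marker-by-tDCS, marker-by-exercise and the baseline value of that outcome. Marker by combined versus double control is an acceptable alternative.
- Define the marker as the visit 1.1 value, taken before the first conditioning session. The visit schedule supports this: "At visits 1.1, we will conduct assessments of pain, quality of life, TPSP, CPM, TMS and EEG acquisition". Visits 1.3 and 2 come after arm-specific conditioning has begun, and visit 2 has no pain assessment.
- Label the analysis exploratory, report interaction estimates with 95% CIs, and base any statement about response prediction on them. Describe the plain correlation as prognostic only.
- Include treatment arm in the change-with-change analyses.

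The cost is analysis-plan wording; no new data or visits are needed. The price is imprecision: the intervals will be wide, the roughly 10% false-positive chance applies to each marker and outcome, and predictor claims will be harder to make.
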